Because the bilateral montage delivered 2mA to each anode electrode over the left and right DLPC, finding superior results for the unilateral 4mA condition could be related to the involvement of the right DLPFC being stimulated, or due to a stronger intensity level being administered. The study proposed here will investigate the latter hypothesis: results were due to a more vigorous tDCS intensity (i.e., 4mA).

METHODS:

Sample

Based on pilot data, we expect a pooled standard deviation for response time on the N-Back test of 3,000 ms and a correlation of 0.89 between adjacent time points (pre, post, follow up). For 80% power to detect a difference across the three levels of intensity, while also accounting for the sex of a participant, a repeated-measures ANOVA test at an alpha level of 5% will require 54 participants with AD (27 men and 27 women). To compensate for anticipated attrition over the study, we will recruit a sample of 30 men and 30 women, 60 total, randomized into the three treatment arms. These participants would have received the diagnosis of probable AD from Baycrest's Memory Clinic expert staff [32, 33] according to standard clinical criteria. Only patients with no family history of epilepsy and who can give consent will be tested. We will seek people with mild to moderate AD (Reisberg stages 3, 4, or 5, [34]). Participants must show no history of stroke or traumatic brain injury, nor shunts or metal in the head that could interfere with the delivery of tDCS. Finally, people will have no evidence of significant heart disease, alcoholism, drug use. All

enrolled participants will be expected to complete an MRI; however, if they are unable to complete an MRI due to the presence of an exclusion criterion, they will still be allowed to complete all subsequent stages of the study. In the initial assessment, we will verify participants can complete the study task (N-Back). Only individuals able to complete this task will be allowed to complete the study.

Recruitment and Pre-Assessment

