Stimulation will be delivered for 20 minutes concurrent with the beginning of the session, with the anode electrode placed over the left DLPC and the cathode over the right DLPC.

Figure 1 (below). Dorsolateral Prefrontal Cortex Montage. Activation prediction based on modeling software from Soterix HD-Explore; color gradients reflect increasing levels of predicted intensity, where red reflects a peak intensity of 0.61 mA.

Study Design

Participants will be randomized into three treatment arms. Participants will complete three rounds of executive function training in each arm, with each round paired with different stimulation intensity (SHAM, 2mA, 4mA). The below flowchart displays the procedure that participants will follow:

Initial Assessment

In the first week, all participants will receive an initial assessment to gather demographic information (age, sex, years of education, racial background, and hand preference) and conduct a formal evaluation of participants. Evaluation includes the Montreal Cognitive Assessment (MoCA; [26]) and the Mini-Mental State Exam (MMSE; [27]) to assess the level of cognitive function, as well as a practice version of the study task (N-Back) where they must state via a button press on a computer if the presented image is the same or different from the previous image. This is to ensure the participants can complete it in the upcoming study rounds. From these tasks, participants' impairment scores will be calculated. *Cognitive severity* will be measured as the combined total from the MoCA and MMSE ($x/30 + x/30$). In contrast, *baseline severity* will be measured as the

average response time on the practice version of the N-Back. Assuming inclusion criteria are met, participants in the first week will also complete a structural MRI [view MRI protocol – page 11]. We will use SPM 12 to quantify head and tissue layers, including CSF, which will be quantified relative to the participant's skull size. For skull thickness and grey matter, we will quantify regions around the left DLPFC.

Baseline Evaluation

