give sham or tDCS set at 2mA or 4mA for 20 minutes and will remain during the session with the participant for safety precautions and troubleshoot any computer problems. Simultaneously with the stimulation, participants will use the computer to practice the given N-back task. This N-back task is modeled off of the 1-back version of the N-back Matching Task [41]. In that study, participants were asked whether a presented digit (e.g., a red 5) was the same as the previously shown digit (either a red five or some other number-color combination); they gave their response by pressing a key on a keyboard to indicate if the number is the same (i.e., a red 5), or different (i.e., something other than a red 5). Following Basak and O'Connell [42], we have created different versions of this task but use images (animals, fruits, vehicles, faces) rather than numbers to make the task slightly easier for people living with dementia. The only difference between these versions is the stimuli presented. We also have normed these versions with normal elderly controls and found that response times and errors were similar for all versions. In each round, participants will practice a different version of the N-Back. Evaluations specific to that round will also administer a round-specific untrained list.

Subsequent Evaluations

For each round, in addition to the evaluation just before the first stimulation session, an additional evaluation will take place during the final training session, and two weeks later after the final session. In this manner, we can obtain a baseline measurement, check for post-stimulation changes, and if those changes have continued two-week's post-stimulation.

Structural MRI Protocol

Participants will undergo a Structural MRI at Baycrest. The protocol has been informed to the MR Technicians (please see attached documents). The Project Coordinator will book the MR suite using the Baycrest MR Web Scheduler with a 72 hour notice at the least.

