Participants will be asked to arrive 15 minutes before their scheduled scan to review and fill the consent and MR screening forms. The participant will then be escorted to the Interview room to be interviewed by a Level 11 MR Personnel with respect to their MR screening form and medical history prior to changing for the MR exam. After changing, the MR technologist will escort the research participant into the magnet room and the accompanying researcher (Assistant, Coordinator or PI) to the control area. Post scanning, the lab member accompanying the research participant will monitor the change process, and other processes outlined in the “MR Research Suite Process Bacycrest – RRI.”

To be able to successfully perform the MRI, lab members will undergo the Virtual MR Safety Training & Orientation session and will also receive an in person suite tour.

Planned Analyses

The primary outcome measure will be improvement on an N-Back Task, both a trained version and an untrained version. Improvement will be measured in terms of the average response time (i.e., the amount of time needed to make a response). A repeated-measures ANOVA will be run to compare the three stimulation conditions (SHAM, 2mA, 4mA) with sex (male, female) as a between-subject variable. This analysis will be conducted separately for the trained and untrained items. Scheffé tests will compare the different conditions. We expect to find the greatest improvement in the 4mA condition.

Next, we will calculate a tDCS time improvement score for each participant per condition: the difference between the final average response time on the N-Back task from the last stimulation session subtracted from the baseline response time in each condition. To produce tDCS *effectiveness scores*, the time improvement score in the SHAM round will be deducted from the number calculated in each real tDCS round. In other words:

- Time Improvement in the 4mA condition *minus* Time improvement in the SHAM condition;
- Time Improvement in the 2mA condition *minus* Time improvement in the SHAM condition.

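### The effectiveness scores subtract every round's baseline in full; adjusting for those baselines would give more precise intensity contrasts from data already collected

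*Protocol*

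**What the plan says.** Study Design gives each participant three training rounds, "with each round paired with different stimulation intensity (SHAM, 2mA, 4mA"), so every intensity comparison is within person. A baseline exists for every round: Subsequent Evaluations says "For each round, in addition to the evaluation just before the first stimulation session", there is an evaluation at the final session and another two weeks later.

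Planned Analyses then does two things.

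- **Primary analysis.** "The primary outcome measure will be improvement on an N-Back Task, both a trained version and an untrained version", expressed as average response time. A repeated-measures ANOVA is to "compare the three stimulation conditions (SHAM, 2mA, 4mA) with sex (male, female) as a between-subject variable". No other term is named, and no formula for improvement is given at this point.
- **Individual-differences analysis.** The time improvement score is the final response time "from the last stimulation session subtracted from the baseline response time in each condition". To form the effectiveness scores, "the time improvement score in the SHAM round will be deducted from the number calculated in each real tDCS round". These scores are the dependent variables of the regression on brain measures, impairment and sex.

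The only baseline among the predictors is baseline severity, which Initial Assessment defines as the response time on a practice N-Back. It is one value per person.

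**The concern.** An effectiveness score is a difference of two differences: two final values and two round baselines, each with a coefficient of 1 or -1. In a parallel-group trial, subtracting the baseline removes stable differences between people. Here the contrast between a person's own rounds already removes them. What the round baseline can still usefully carry is that round's departure from the person's usual level, and the best weight for it is less than 1. Using a weight of 1 over-corrects and adds the error of both baselines to the contrast.

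Baseline severity does not help, because a value that is constant across rounds cannot adjust for round-to-round differences. At stake is precision in a trial sized at 54 completers, above all in the individual-differences regression, which relates several predictors and sex interactions to this score.

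**Working it through.** **Inputs.** From the Sample section: "we expect a pooled standard deviation for response time on the N-Back test of 3,000 ms" (SD below), and "a correlation of 0.89 between adjacent time points (pre, post, follow up"). I take r = 0.89 as the correlation of baseline and final session within a round. Not in the protocol: c, the correlation between response times from different rounds. I vary c and assume equal SDs and one c for all pairs of rounds.

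**The protocol's own figure.** The 54 cannot be reproduced, because no effect size is stated. The 60 to be recruited agrees with 54/(1 - 0.10), but the attrition rate is not stated either. The variance results do not depend on these figures.

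**Step 1, change score.** Each round's change has variance 2 SD²(1 - r). The covariance of the changes from two rounds is c - c - c + c = 0. The active-minus-SHAM contrast therefore has variance 4 SD²(1 - r) = 4 × 0.11 SD² = 0.44 SD², an SD of 1,990 ms per person, whatever c is.

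**Step 2, adjusted.** The final-session difference and the baseline difference each have variance 2 SD²(1 - c), and their covariance is 2 SD²(r - c). The best slope is k = (r - c)/(1 - c), and the remaining variance is 2 SD²(1 - c)(1 - k²) = 2 SD²(1 - r)(1 + k).

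**Step 3, ratio of adjusted to change.** (1 + k)/2 = 1 - (1 - r)/(2(1 - c)). This is below 1 whenever k is below 1.

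| c (assumed) | slope k | adjusted SD, ms | ratio | reduction | ratio in two simulations, n = 54 |
|---|---|---|---|---|---|
| 0 | 0.89 | 1,934 | 0.945 | 5.5% | 0.95, 0.97 |
| 0.5 | 0.78 | 1,877 | 0.89 | 11% | 0.91, 0.90 |
| 0.7 | 0.633 | 1,798 | 0.817 | 18% | 0.85, 0.81 |
| 0.8 | 0.45 | 1,694 | 0.725 | 27% | 0.73, 0.71 |

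The simulations estimate the slope, so they include its small cost. The row c = 0 is the familiar parallel-group result: (1 - 0.89²)/(2(1 - 0.89)) = 0.2079/0.22 = 0.945. It would require that a person's speed in one round says nothing about the next.

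**Step 4, carry-over.** Suppose earlier stimulation shifts a round's baseline by λ, and a fraction g of the shift is left at the final session. The change contrast is then off by (g - 1)λ and the adjusted contrast by (g - k)λ. With k = 0.633 (c = 0.7):

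- g = 1 (undiminished): change 0, adjusted 0.37λ
- g = 0.5: change -0.5λ, adjusted -0.13λ
- g = 0 (gone): change -λ, adjusted -0.63λ

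Neither method dominates. For scale, take g = 1, a 4mA carry-over of 0.2 SD, and cyclic orders in which SHAM directly follows 4mA in two orders of three (all assumptions). The adjusted 4mA-SHAM bias is 0.2 × 2/3 × 0.367 = 0.049 SD, about 147 ms. The mean squared error is 0.817 × 0.44/54 + 0.049² = 0.0091 SD², against 0.44/54 = 0.0081 SD² for the change score, so adjustment is about 11% worse (about 8% in a simulation). At 0.1 SD adjustment is about 11% better.

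**The case against.** **Scope.** The change formula is introduced for the follow-on regression, not for the primary ANOVA. A reader might infer that the protocol fixes the primary comparison as the same change score. It does not: the outcome there is described only as improvement in average response time, and the Sample section speaks of three time points, which could mean a condition-by-time test. This stands as a limit on the claim. It does not remove the point, because an ANOVA of improvement with condition and sex alone lets no round baseline enter with an estimated slope.

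**Size.** The between-round correlation is not given. Each round uses a different N-Back version and its own untrained list, which could lower it. This also stands: only the direction is firm.

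**Relevance to the regression.** The ratios above concern the intensity contrast, not the coefficients of the predictors, and the protocol calls the model a logistic regression although the score is continuous. The ratios are therefore a guide to the noise in the outcome, not to the precision of each predictor's coefficient.

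**Preference.** A change score is valid, matches the hypothesis about degree of improvement, and covariates are often left to an SAP. That would answer a protocol that was silent. This one writes the score out and builds its dependent variables on it.

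**Carry-over.** If an earlier effect persists undiminished through the next round, full subtraction cancels it and adjustment keeps part. This is a genuine cost of the change. It reverses when the effect halves or vanishes by the final session, so it is a reason to report both analyses and not a reason to keep full subtraction alone.

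**Conclusion.** The point holds as a recoverable loss of precision. It is explicit for the effectiveness scores and follows for the primary ANOVA on its natural reading. With r = 0.89, adjustment lowers the variance of an intensity contrast by about 5% (c = 0), 10% (c = 0.5), 15 to 18% (c = 0.7) or 27% (c = 0.8). These figures assume equal SDs and a between-round correlation that the protocol does not state.

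Two stronger readings are not supported. First, a reader might infer that the planned analysis is biased. It is not biased by the choice of slope; bias arises only through carry-over, and that can go against either method. Second, a reader might turn the reduction into a stated gain in power or participants, for example 54/0.89 = 61 or 54/0.817 = 66 people. Such figures are illustrative only: the Sample section gives no effect size and does not say which form of the outcome was powered.

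**What to change.** - **Intensity comparison.** Analyse the final response time of each round in a mixed model with intensity, round, sex, sex by intensity and a person effect. Add baseline response time as a covariate, split into the person's mean over rounds and that round's deviation from it. Run it separately for trained and untrained items, as planned.
- **Individual differences.** Model the final-session difference (active minus SHAM) as a continuous outcome, with the corresponding baseline difference as a covariate beside the planned predictors; once for 4mA and once for 2mA.
- **Sensitivity.** Keep the plain change score, and say in advance that a disagreement between the two may reflect carry-over.

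The cost is a change of analysis wording and one or two extra model terms. No new data are needed, since every round already has a baseline. The downside to record is that carry-over lasting undiminished through the next round stays partly in the adjusted contrast, while carry-over that decays within the round distorts the change score more. The change should be fixed before unblinding.

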tDCS studies typically report significant group effects despite the variability demonstrated among participants, with some showing clear, meaningful improvement, while others only show statistical improvement or none at all. These variable results may be related to the conventional stimulation intensity level of 2mA. Recent evidence suggests an electric field of at least one v/m is needed to affect local networks in the brain [15] reliably. However, tDCS at 2mA produces an electric field around only 0.6 v/m because a large amount of shunting (a dilution of the incoming current) occurs as the current travels from the electrode on the scalp, through the skin, skull, and cerebral spinal fluid (CSF), before reaching the brain. The most direct way to increase the electric field produced in the brain is to increase the intensity delivered. Current tDCS machines can have an intensity level of 4mA, resulting in more substantial electric fields than one v/m. We predict that if we were to administer tDCS at 4.0 mA, a more significant number of participants would show a meaningful response, and those who improve at 2mA may improve even more from 4.0mA due to having a larger electric field produced.

We aim to test this hypothesis in people with Alzheimer's Disease because they have unique attributes that may impact tDCS differently from other populations. More specifically, the amount of shunting is predicted to be larger due to increasing CSF from brain atrophy [16]. Thus, 2mA may be too weak to be very effective in some people with Alzheimer's Disease due to the higher level of shunting. More significant improvements would be observed from a higher intensity level that can

better interact with the remaining cortex. Alzheimer's Disease is also predominately female, and past studies have suggested men and women respond differently to tDCS [17-24]. For example, women have smaller skulls than men in general, which are predicted to receive more of the incoming stimulation. Finally, as Alzheimer's Disease is progressive, the degree of impairment may be relevant [25]. We will check if individuals who are more impaired benefit more when the stimulation intensity is set higher. The level of impairment will be measured in two ways: (1) the baseline score on the task training in the study (baseline severity); and (2) scores collected from cognitive testing (cognitive severity).

Purpose of the Research

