Demonstrating results are possible with 4 mA, which may be superior or unachievable with 2 mA, would persuade other researchers to also explore if the improvement (or the lack thereof) in their own tDCS studies would be present or larger using 4 mA tDCS. Over time, just as tDCS researchers began favouring 2 mA over lower intensity levels, 4 mA rather than 2 mA could become the new convention. Also, by exploring how individual differences impact the response observed, we can target those individuals who are expected to most benefit from tDCS. In this manner, tDCS studies can become more efficient.

[figure not shown]
Hypotheses Addressed

- The degree of improvement observed in people with Alzheimer's disease will be significantly greater when training is carried out at higher stimulation intensity (4mA vs. 2mA, SHAM).
- There will be significantly more significant improvement observed when:
 1. individuals have more atrophy (decreased brain volume, higher CSF volume).
 2. Individuals have a higher degree of impairment.
 3. The participant is female.

PRELIMINARY STUDIES

The proposed study models after our original three-round study [5] where three different tDCS montages were compared for improving naming ability. We recently completed another three-round study [31] where a mixed group of people with dementia (AD and FTD) concluded three consecutive rounds of executive function training with either: 4mA tDCS targeted towards the left dorsolateral prefrontal cortex (DLPFC), 2mA tDCS via two anode electrodes to the left and right DLPC respectively, or SHAM stimulation, which is the accepted placebo condition in tDCS studies. In SHAM stimulation, tDCS is only briefly active at the beginning and end of the session, which mimics the real-life sensation of tDCS as feelings are felt mainly only at the beginning and end of the session when the current is ramping up or down. We measured how much participants improved on an N-Back task, defined as having faster response times. For evaluation, participants completed two versions of this N-Back task: one practiced during the tDCS sessions, and another never practiced and was only given during evaluations. For trained items, results were similar regardless of stimulation condition, but the most significant improvement was found for the 4mA condition for untrained items.

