Thus, a tDCS effectiveness score is calculated for each participant in the 4mA and 2mA conditions. These tDCS effectiveness scores will then be the dependent variables in a multivariate logistic regression; once for trained items, again for untrained items. The predictors will be the CSF level of a participant, grey matter volumes and skull thickness around the DLPFC, impairment scores (baseline and cognitive severity), and interactive terms representing the sex of the participant. In this manner, we can examine what individual differences predict the tDCS response in people with AD and if these predictors are the same for two and 4mA tDCS while checking for sex differences. We expect more significant levels of CSF, less DLPFC grey matter, thicker skulls, and greater impairment levels will be predictive of more substantial improvement in the 4mA condition. CSF and grey matter values may be less predictive for how well women respond to tDCS as their relatively smaller heads could compensate for increased shunting levels. Finally, a 2 (male AD, female AD) x3 (4mA, 2mA, SHAM) between-subject repeated measures ANOVA will be run for tasks administered in evaluation: MoCA scores, to check for changes in general cognition, as well as for verbal fluency, digit span, and Corsi to check for generalized executive function differences. These analyses are exploratory.

Funding

This study is supported by BrightFocus Foundation, which reviewed the submitted protocol, and awarded funds to [name] [name] towards completing the proposed study.

Risks

The tDCS protocol for this experiment was determined according to the best practices observed in previous research using tDCS stimulation [45]. Furthermore, tDCS is safe, has virtually no side effects,

is technically easy to carry out, and is not uncomfortable to undergo [46,47]. Multiple studies have also reported that the administration of 4 ma tDCS has no more adverse effects than 2 ma tDCS [48]. No incidence of seizure has been recorded, although side effects could include headache, drowsiness, itching sensation, nausea, and, in rare cases, disorientation. In our experiences, the only observed and reported side-effect has been temporary redness post-stimulation where the sponge was placed, as well as the occasionally reported headache.

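### The individual-difference analysis names a logistic regression for scores that the protocol defines as continuous differences in milliseconds

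*Protocol*

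**What the plan says.** All of this is in the Protocol; where no other section is named, the text is under Planned Analyses.

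- **Outcome.** Improvement is measured by average response time. For each condition, the time improvement score is baseline response time minus the response time at the last stimulation session. The effectiveness score at 4 mA is "Time Improvement in the 4mA condition *minus* Time improvement in the SHAM condition", and the 2 mA score is built in the same way.
- **Model.** "These tDCS effectiveness scores will then be the dependent variables in a multivariate logistic regression; once for trained items, again for untrained items".
- **Predictors.** CSF level, prefrontal grey matter, skull thickness, baseline severity and cognitive severity, together with "interactive terms representing the sex of the participant".
- **Expected result.** More CSF, less grey matter, thicker skulls and greater impairment "will be predictive of more substantial improvement in the 4mA condition".
- **Hypotheses Addressed.** The second group opens with "There will be significantly more significant improvement observed when" and then lists greater atrophy, greater impairment and female sex.
- **Rationale.** The authors predict that at 4 mA "a more significant number of participants would show a meaningful response". They do not say what makes a response meaningful.

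**The concern.** The sentence that names the model makes the scores themselves the dependent variables, not a class derived from them. A score formed by subtracting one response-time difference from another can take any value, positive or negative. An ordinary logistic regression cannot use it.

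Two repairs are possible, and they answer different questions. A linear model asks how much improvement changes with atrophy or impairment. A logistic model on a dichotomised score asks who passes a threshold, and the answer depends on where the threshold lies. If the protocol leaves this open, both the choice of model and the choice of cut could be made after the data are seen, for two scores and two item sets.

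This regression is the only planned test of the atrophy and impairment hypotheses. It is also the only test of the prediction that CSF and grey matter matter less in women, and of whether the same predictors operate at 2 mA and 4 mA. The sex hypothesis has a second route, because sex is a between-subject factor in the primary ANOVA.

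**Working it through.** The protocol gives no sample size, power or effect size for this regression, so there is no stated figure to reproduce. The 54 participants (60 recruited) were derived for the repeated-measures ANOVA.

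**1. Type of outcome.** Write RT for average response time.

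- Improvement in a round: I = RT(baseline) − RT(last session), in ms.
- Effectiveness at 4 mA: E4 = I(4 mA) − I(SHAM).
- Effectiveness at 2 mA: E2 = I(2 mA) − I(SHAM).

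E4 and E2 are continuous and can be negative. As a check, a binary logistic model was tried on simulated scores of this kind (n = 54, mean 500 ms, SD 1,500 ms, five predictors). It stopped with an error because the outcome lay outside the interval 0 to 1. A linear model on the same data ran.

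**2. Spread of the score.** Under Sample the protocol states: "we expect a pooled standard deviation for response time on the N-Back test of 3,000 ms and a correlation of 0.89", the correlation being between adjacent time points. With equal SDs at both times:

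- SD(I) = 3,000 × √(2 × (1 − 0.89)) = 3,000 × √0.22 = 1,407 ms.
- SD(E) = 1,407 × √(2 × (1 − c)), where c is the correlation of improvements between two rounds. The protocol does not give c, so it is assumed.

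| c (assumed) | SD(E) |
|---|---|
| 0 | 1,990 ms |
| 0.25 | 1,723 ms |
| 0.5 | 1,407 ms |

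The definition in step 1 already establishes that the score is continuous. This step only shows its scale.

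**3. Which reading the text supports.**

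| Place | What it speaks of | Model it implies |
|---|---|---|
| Planned Analyses, score definition | a difference in ms | linear |
| Hypotheses Addressed, second group | amount of improvement | linear |
| Planned Analyses, expected result | more substantial improvement | linear |
| Rationale | number of people with a meaningful response | responder, no threshold given |
| Planned Analyses, model sentence | logistic regression | categorical outcome |

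**4. Which repair suits the sample better.** This does not measure the defect; it only helps to choose between repairs. The protocol does not say how many sex interactions it intends. Assume one measure per predictor and a main effect of sex:

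- Interactions with CSF and grey matter only: 5 + 1 + 2 = 8 terms.
- Interactions with all five predictors: 5 + 1 + 5 = 11 terms.

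At n = 54:

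- Linear model, residual degrees of freedom: 54 − 8 − 1 = 45, or 54 − 11 − 1 = 42.
- Dichotomised score: the smaller outcome group is at most 54 / 2 = 27, which gives 27 / 8 = 3.4 or 27 / 11 = 2.5 participants per term. Any uneven cut gives fewer.

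The number analysed could also fall below 54, because the Sample section lets people who cannot have an MRI continue, and they would lack the imaging predictors.

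**The case against.** The strongest reply is that this is a one-word slip. Every sentence tied to the regression concerns the amount of improvement. The Rationale sentence about a meaningful response compares the number of responders at the two intensities and is not about the regression. On that view there is no real choice of estimand, and a binary logistic fit would fail at once, so a silently wrong result is unlikely. Most of this stands. It makes linear the natural repair, but the sentence still names the wrong model for a hypothesis test.

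A second reply is that a responder threshold may properly be left to the SAP. That is fair, and the absence of a cut-point is not an omission in itself. But a SAP that added one would analyse a different outcome from the one the protocol names, and a SAP that used a linear model would depart from the protocol's model. The protocol sentence needs correcting either way.

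Third, an ordinal (cumulative) logistic model can technically take a continuous outcome. That is true, but the protocol names no such model, so the claim that the analysis cannot be fitted holds for logistic regression in its ordinary sense.

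Fourth, the label of exploratory at the end of that paragraph might be read as covering the regression. It follows the ANOVAs of the other cognitive tasks and does not clearly reach back. Even an exploratory analysis needs a model that fits its outcome.

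Finally, the participants-per-term figures rest on an assumed count of terms and describe a dichotomised model that the protocol does not propose. That is correct, and they serve only as a reason to prefer the linear repair.

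**Conclusion.** The point holds. The outcome is continuous by the protocol's own definition, the named model needs a categorical one, and nothing in the document links the two. The word is most likely a mistake for linear, although the text does not settle it.

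The defect is confined to the individual-difference analysis. It leaves the primary ANOVA and its sample size untouched. No power figure is affected, because the protocol states none for this regression. What is at risk is a choice of model or cut-point after the data are seen, in the only planned test of two stated hypotheses. It should be fixed, but it does not threaten the trial's main comparison.

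The mismatch rests on the text alone. Only the SD range (equal SDs, c from 0 to 0.5) and the term counts (8 to 11) depend on assumptions.

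**What to change.** Replace the model sentence under Planned Analyses with:

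> The two effectiveness scores (continuous, in ms) will be the dependent variables in a multivariate linear regression, fitted once for trained items and once for untrained items.

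Keep the listed predictors and the sex interactions. If a responder analysis is also wanted, in line with the Rationale, make it secondary and fix its cut-point before the data are seen.

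One optional addition, which does not correct an error: the protocol wants to know whether predictors are the same at the two intensities. It could say that this will be tested by the equality of each predictor's two coefficients in the joint model. Since E4 − E2 = I(4 mA) − I(2 mA), an equivalent is to regress the 4 mA minus 2 mA improvement on the same predictors.

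The cost is protocol wording only, with no new data and no change to the sample size or the primary ANOVA.
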